# 6.5 Clinical and epidemiological data

#### 6.5.1 Quality control

Clinical data is recorded using an electronic case report form (eCRF) or databases (e.g. fitness tracker). The eCRF data entry includes a plausibility check. Data will be harmonised by the data analyst prior to exploration and missing data, and patterns thereof, will be explored.

#### 6.5.2 Exploratory analysis

Data normality will be thoroughly visualised and summarised prior to analysis. The data distribution, including distribution of missing data, will be evaluated.

#### 6.5.3 Secondary endpoint reporting

Paired analysis (ITT) will be conducted for baseline and month 6 measurements. As with the primary endpoint, PP or above/below median compliance score subgroup analysis may be additionally constructed. Linear-mixed effects models will be constructed to explore heterogeneity in responses among participants and leverage the strength of our longitudinal data. In addition, descriptive statistics relating to change to baseline can be reported. The following outcomes will be assessed:

- body mass index  $(kg/m^2)$ , diet arm of the study
- fat-free body mass (%), diet arm of the study
- current smoking ("yes" or "no", binary response, can be analysed using a generalised estimation equation or generalised linear mixed model with a log link function)
- vascular health parameters
  - pulse wave velocity (mm/s)
  - intima-media thickness (mm)
  - plaque score
- physical activity
  - international physical activity questionnaire (IPAQ) score
  - average daily steps per week
  - active minutes per week
- abdominal fat composition, diet arm of the study
  - visceral fat (mm)
  - subcutaneous fat (mm)
- heart rate variability (ms)
- resting heart rate (beats per minute)
- sleep quality score (fitness tracker, average score per week)
- subgroup in diet arm of the study:  $\beta$ -hydroxybutyrate levels

- pulmonary health, including FEV1, FVC, and FEV1/FVC
- ergonometry functional values

Data will be reported using spaghetti plots (visualising individual values) and/or tables of mean and standard deviations. In the diet arm, changes in body mass index, fat-free body mass, and abdominal fat composition may also be compared between groups (with and without ketogenic supplement) using Wilcoxon testing of delta change, or via inclusion of ketogenic supplement covariate in linear mixed models.

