#### 3.7 Hypothesis framework

For each of the primary, secondary, or subsidiary outcomes, the null hypothesis is that there is no true difference in effect between the baseline measurement and the measurement taken at 6 months.

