# 4 Study population

#### 4.1 Eligibility

#### 4.1.1 Inclusion criteria

- 1. Women aged 30 to 60
- 2. Motivated to change their lifestyle
- 3. Smoking cessation:  $\geq 10$  cigarettes per day for at least the last five years
- 4. Dietary intervention: BMI between 25 and 35
- \* Should 3 and 4 apply, the participant will be allocated to the smoking cessation group.

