#### Clinical and epidemiological endpoints

- body mass index (BMI), diet arm of the study
- body composition (muscle, fat, water), diet arm of the study
- smoking status, *smoking arm of the study*, including

- current smoking (yes/no)

- cigarettes in the last 7 days
- use of nicotine replacement products
- vascular health

pulse wave velocity, intima-media thickness, and plaque score before and after intervention

- abdominal fat composition, *diet arm of the study* visceral and subcutaneous fat before and after 6 months of intervention
- physical activity and health measured using the international physical activity questionnaire (IPAQ), sports examination (VO2max), and fitness tracker (daily steps, active minutes, floors climbed); resting heart rate
- pulmonary health

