# 8 Publication outline

For each sub-study (smoking cessation and intermittent fasting), one main paper will be prepared describing the overall effects on a variety of organ systems. Key aspects to epigenetic and clinical effects will be presented in the main data, while additional outcomes may be presented in supplementary data, although this will need to be confirmed.

For each study, a participant flowchart diagram as well as overview for compliance will be shown. The following characteristics will be described for all participants at the beginning (and at the end) of the study, separately for each intervention:

- age
- ethnicity
- highest education
- menopausal status
- parity
- use of menopausal hormone replacement therapy (postmenopausal only)
- use of oral contraceptives
- body mass index  $(kg/m^2)$
- body composition from bioelectric impedance analysis (% mass), diet group only
- abdominal fat (visceral and subcutaneous, both in mm)
- resting heart rate
- smoking status (current/ex/never smoker)
- smoking pack year

Data will be reported in a table, describing the parameters using mean or median and standard deviation or quantiles, respectively, or proportions (%) depending on data type and distribution.

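### Diet-arm body composition is analysed only as fat-free mass in per cent, so a loss of lean mass could go unseen or be read as a gain; absolute fat-free and fat mass should be analysed beside it

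*SAP*

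**What the plan says.** Section 5.4.2, under the clinical and epidemiological endpoints, lists "body composition (muscle, fat, water), diet arm of the study" without a unit. Section 6.5.3, which fixes the analysis, carries this forward as a single item: "fat-free body mass (%), diet arm of the study". BMI and abdominal fat (visceral and subcutaneous, in mm) are separate outcomes in the same list. Muscle and water have no entry there.

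The analysis is before-after: "Paired analysis (ITT) will be conducted for baseline and month 6 measurements". A comparison of the supplement arms is optional: "changes in body mass index, fat-free body mass, and abdominal fat composition may also be compared between groups". That sentence gives fat-free mass no unit.

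Section 8 lists "body composition from bioelectric impedance analysis (% mass), diet group only" among the participant characteristics to be described. This shows how composition is measured and on what scale it is reported. It is not an analysis.

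Section 3.7 frames every outcome without direction: "the null hypothesis is that there is no true difference in effect between the baseline measurement and the measurement taken at 6 months".

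**The concern.** Fat-free percentage is 100 minus fat percentage. It describes the make-up of the body relative to its current weight and does not show how much lean tissue is present. When weight changes, numerator and denominator move together, so a rise can mean that lean mass was kept, gained or lost.

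Weight change is a live possibility in this arm. The entry criterion is "Dietary intervention: BMI between 25 and 35", section 6.4.2 uses change in BMI to colour plots, and the microbiome analyses relate shifts to weight loss. A before-after rise in fat-free percentage could then be taken as a favourable change in lean tissue when lean mass had fallen.

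The same applies to the supplement comparison, one of the few randomised contrasts in the study. An arm that loses more fat can show the larger rise in percentage while also losing more lean mass. In addition, the endpoint named in 5.4.2 is only partly carried into 6.5.3.

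**Working it through.** The SAP gives no figure for body composition, so there is nothing of its own to reproduce. The check is an identity, followed by illustrations on assumed inputs.

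**Identity.** Let W be baseline weight, f the baseline fat-free fraction, L the weight lost and q the share of L that is fat-free.

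- Fat-free mass changes by −qL, so it falls whenever q > 0.
- The new fat-free fraction is (fW − qL)/(W − L).
- The change in fraction is (fW − qL)/(W − L) − f = (f − q)L/(W − L).

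The percentage therefore rises if and only if q < f. It is unchanged at q = f and falls at q > f.

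**Single participant** (assumed: W = 80 kg, f = 0.60, so 48 kg fat-free; L = 6 kg).

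- 2 kg of the loss lean: (48 − 2)/(80 − 6) = 46/74 = 62.2%. Up 2.2 points, with 2 kg of fat-free mass lost.
- 3 kg of the loss lean: (48 − 3)/74 = 45/74 = 60.8%. Up 0.8 points, with 3 kg lost.
- The percentage falls only if more than 0.60 × 6 = 3.6 kg of the loss is lean.

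**Two arms** (assumed: both start at 80 kg and 60% fat-free).

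| Arm | Weight lost | Lean lost | Fat-free % at month 6 | Fat-free mass at month 6 |
|---|---|---|---|---|
| A | 6 kg | 2 kg | 46/74 = 62.2 | 46.0 kg |
| B | 3 kg | 0.5 kg | 47.5/77 = 61.7 | 47.5 kg |

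Arm A has the higher percentage but lost four times as much lean mass (2/0.5 = 4).

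**Range** (assumed: height 1.65 m, BMI 30, hence 30 × 1.65² = 81.7 kg; baseline fat-free 55 to 70%; weight loss 3 to 10%).

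| Lean share of the loss | Change in fat-free % (points) | Fat-free mass lost (kg) |
|---|---|---|
| 10 to 40% | +0.46 to +6.67 | 0.25 to 3.27 |
| 60%, baseline fat-free 60% | 0.00 | 1.5 to 4.9 |
| 80% | −0.31 to −2.78 | 2.0 to 6.5 |

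The last row shows that the rise is conditional: with a large enough lean share the percentage does fall.

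**What an absolute scale shows.** Take the same height and BMI, 60% fat-free, 5% weight loss (4.1 kg) and a 25% lean share. The percentage rises from 60.0 to 61.8. Fat-free mass falls from 49.0 to 48.0 kg, and fat-free mass index (BMI × fat-free fraction) falls from 30 × 0.60 = 18.0 to 28.5 × 0.618 = 17.6 kg/m².

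**The case against.** The strongest reply is that the percentage is a legitimate measure of relative composition and that the SAP never sets out to measure preservation of lean tissue. No objective, hypothesis or success rule concerns it, and the study's only success rule is for the methylation scores. This stands. It is a reason to keep the percentage and not to demote it to a purely descriptive role.

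A reader might infer that muscle loss would be reported as an improvement. The documents do not support that. No direction of benefit is set for this outcome, the null in 3.7 is two-way, and fat-free mass is not muscle, since it also contains water, which 5.4.2 lists separately.

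A reader might also infer that the misleading rise is the usual case. The SAP states neither an expected weight loss nor a lean share nor a baseline fat-free fraction, so its frequency cannot be derived from the document.

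It can further be said that BMI and abdominal fat are analysed in the same women and that the arm comparison is optional. Both are true, and both limit the harm. Fat-free mass index could be derived from BMI and the percentage, but the SAP specifies no such derivation. Separate tests of BMI and of fat-free percentage do not yield the change in lean mass or its confidence interval, because that change depends on the product of the two within each participant.

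**Conclusion.** The point holds in a limited form. Section 6.5.3 narrows the muscle, fat and water endpoint of 5.4.2 to one relative measure, and that measure cannot separate lean tissue kept from lean tissue lost when weight falls. The identity is exact. The kilogram and percentage-point figures rest on assumed body weight, fat-free fraction, weight loss and lean share, none of which the SAP gives. Under those assumptions, with a lean share of 10 to 40%, the percentage rises by 0.46 to 6.67 points while 0.25 to 3.27 kg of fat-free mass is lost.

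The consequence is a possible misreading: lean loss could go undetected or be taken as a gain, and the two supplement arms could be ranked differently from their absolute lean loss. It concerns one of many secondary outcomes in a study that the SAP describes as predominantly exploratory, and it leaves the primary endpoint untouched. Minor severity, worth correcting because the correction is nearly free.

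**What to change.** In section 6.5.3, next to the percentage, add change from baseline to month 6 in absolute fat-free mass and fat mass. Compute each per participant as the impedance percentage times body weight at the same visit (kg), or times BMI (kg/m²), and fix one of the two scales in advance. Report both changes with 95% confidence intervals, as section 5.1 already promises for effect estimates, before-after and in any comparison of the randomised supplement arms. State the unit in the sentence on that comparison.

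Align the components with 5.4.2: either give muscle and water an analysis in 6.5.3 or say that they will only be described.

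The cost is SAP wording and one or two more secondary outcomes to report. BMI already requires weight and the impedance percentage is already planned, so no new measurement is needed.

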# 6.6 Microbiome data

The following questions will be addressed:

1. How do intermittent fasting or smoking cessation influence the gut microbiome? Is there a shift in dominant types? Is there an increase in species richness? Is there an increase in the relative abundance of genera associate with a healthy phenotype, or loss of species associated with a disease phenotype?

A comparison will be conducted between month 0 and month 6. Data will be analysed in association with the compliance score, as well as epigenetic markers and BMI. Beneficial species include probiotic and short-chain fatty acid producing microbes:

- *Lactobacillus reuteri*, which produces reuterin, a protein oxidant that helps to protect against colorectal cancer.
- *Parabacteroides distasonis*, which can increase levels of unconjugated bile acids that activate GLP1 and UCP1 pathways and improve the glucose and energy metabolism.
- Akkermansia muciniphilia, which induces mucin production necessary for intestinal integrity. This can also be associated with blood markers of LBP, an indicator of gut integrity.

Conversely, harmful microbiobes include species such as *Clostridium difficile*.

- Can the microbiome be used to distinguish lean from overweight or obese individuals, using fecal microbial taxonomic composition? Taxonomic composition of individuals with BMI below and above 25 will be analysed at month 0. The potential species contributing to difference may be analysed using PCA and correlation analysis.
- 3. Can the microbiome be used to distinguish smokers from non-smokers? Taxonomic composition of smokers and non-smokers will be analysed, with the caveat that non-smokers are all of BMI above 25 which may have an impact on microbiome (see above).
- 4. Are the changes in the microbiome associated with predicted functional alterations?

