#### 1. Smoking cessation (n = 60)

Sixty women aged 30-60 without a significant prior medical history who have been smoking above or equal 10 cigarettes a day for at least five years will be recruited and instructed to stop smoking via a professional smoking cessation programme (provided by Suchthilfe Tirol) and 1:1 personal coaching.

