#### Molecular endpoints

• epigenetic markers

DNA methylation-based disease risk, ageing, and exposure signatures in cervical, buccal, and blood samples.

- microbiome
  - changes in overall diversity and proportions of certain beneficial or harmful microbial species in fecal microbiome depending on the intervention
  - distinction of health and lean individuals using microbiome
  - distinction of smokers and non-smokers using microbiome
  - shift in dominant types and association with weight loss
  - potential changes in functional prediction
- *metabolites* alterations in metabolic profile of urine and saliva
- blood profile
  - lipids and HbA1c levels
  - cellular markers of inflammation
  - guided by cellular alterations, targeted investigation of levels of inflammatory cytokines and markers in blood plasma
- ageing markers in the skin and skin barrier function

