#### 6.6.1 Quality control

Barcoded amplicons of the variable V3-V4 region of the 16S rRNA gene will be sequenced on an Illumina MiSeq platform. Paired end fastq files will be demultiplexed and checked for remaining adaptors using FastQC. Further quality control on the raw reads and subsequent generation of Exact Sequence Variants (ESVs) can be done using the DADA2 package in  $R^{.19}$  In short, for each sequence run separately, reads are trimmed and filtered, sequence error rates are estimated, read abundance is calculated after dereplication and read pairs are merged. Next, sequence sets for the different runs are merged, and chimeric sequences and singletons removed. Optionally, spurious ESVs (e.g., relative abundance in no sample  $\geq 0.01\%$ ) can be removed from the final dataset. Taxonomic identification of the ESVs (reliable down to the genus-level) can be performed using the SILVA taxonomic database (version 138) with the RDP naïve Bayesian classifier method.

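### As written, the month 0 microbiome comparison of women with BMI below and above 25 is heavily, though not fully, confounded with smoking, and the SAP gives no restriction, adjustment or caveat for it

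*SAP*

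**What the plan says.** Question 2 of SAP section 6.6 compares lean with overweight or obese women at baseline: "Taxonomic composition of individuals with BMI below and above 25 will be analysed at month 0". Section 6.6.3 reports this through principal component and species plots. The table in 6.16 lists lean versus obese together with the smoker comparison as a baseline microbiome comparison.

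Three rules in section 4.1.1 decide who can be in each BMI group:

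- Diet sub-study: "Dietary intervention: BMI between 25 and 35".
- Smoking sub-study: at least 10 "cigarettes per day for at least the last five years", with no BMI limit stated.
- Women who meet both: "Should 3 and 4 apply, the participant will be allocated to the smoking cessation group".

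Question 3, smokers against non-smokers, is planned "with the caveat that non-smokers are all of BMI above 25". Question 2 has no corresponding statement about smoking.

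On taxonomy, the molecular endpoints in 5.4.2 include "proportions of certain beneficial or harmful microbial species", and 6.6 names individual species as beneficial or harmful. Section 6.6.1 qualifies the 16S method: "Taxonomic identification of the ESVs (reliable down to the genus-level").

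**The concern.** A woman with BMI below 25 can enter only through the smoking criterion, so there are no lean non-smokers by design. The group above 25 consists mostly of diet women, whom 6.6 treats as the non-smokers. Pooling everyone and splitting at 25 therefore compares a group made up entirely of long-term smokers with one in which smokers are a minority. A microbial difference credited to body weight could be partly or wholly a smoking difference.

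The Question 3 caveat rests on the same fact, read in the other direction. The plan warns about it where smoking is the exposure and not where BMI is.

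A smaller matter in the same section is that gains and losses of named species would be reported from assignments that the SAP itself trusts only to genus.

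**Working it through.** **Plan's own figure.** The SAP gives no sample-size or power figure for the microbiome comparison. Its one power statement (3.6: n = 60, difference 0.2, SD 0.44, power 0.94) concerns the methylation indices. It reproduces as a paired comparison at two-sided 0.05: Φ(0.2 × √60 / 0.44 − 1.96) = Φ(1.56) = 0.94. It has no bearing on this point.

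**Inputs.**

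- Planned smoking sub-study: 60 (3.1, "Smoking cessation (n = 60").
- Planned diet sub-study: 120 (3.1).
- Share of smokers with BMI below 25: not given. Assumed, and varied from 10% to 90%.
- Diet women: all taken as non-smokers, as Question 3 treats them. This is also an assumption, because 4.1.1 does not exclude women who smoke fewer than 10 cigarettes a day from the diet arm.
- BMI of exactly 25 is counted in the upper group.

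**Step 1: structure.** Let s be the number of smokers with BMI of 25 or more. The four cells are lean smokers 60 − s, lean non-smokers 0, heavier smokers s, and heavier non-smokers 120.

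**Step 2: share of a smoking effect in the pooled contrast.** Suppose a microbiome measure has a BMI effect b and a smoking effect g that add. The crude difference, lean minus heavier, is then

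b + g × [1 − s/(s + 120)].

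The bracket is the share of the smoking effect carried into the BMI contrast.

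| Lean share of smokers (assumed) | Lean smokers | Heavier smokers (s) | Smokers in group at or above 25 | Share of g carried |
|---|---|---|---|---|
| 10% | 6 | 54 | 54/174 = 31% | 69% |
| 50% | 30 | 30 | 30/150 = 20% | 80% |
| 90% | 54 | 6 | 6/126 = 5% | 95% |

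The correlation (phi) between being lean and being a smoker is 0.26, 0.63 and 0.93 in these three rows.

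**Step 3: can the two effects be separated?** With an intercept, a lean indicator and a smoker indicator, the design matrix has full rank (3 of 3) at every lean share from 10% to 90%. It drops to rank 2 only if all 60 smokers have BMI below 25. In the adjusted model the diet women inform only the non-smoker level, so the lean coefficient equals lean smokers minus heavier smokers. Adjusting for smoking and restricting to the smoking sub-study therefore use the same women for the BMI contrast.

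**Step 4: precision after restriction.** The detectable standardised difference for one continuous measure, at 80% power and two-sided 0.05, is (1.960 + 0.842) × √(1/n₁ + 1/n₂):

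- 30 vs 30: 2.802 × √(1/30 + 1/30) = 0.72 SD
- 18 vs 42: 2.802 × √(1/18 + 1/42) = 0.79 SD
- 12 vs 48: 2.802 × √(1/12 + 1/48) = 0.90 SD
- 6 vs 54: 2.802 × √(1/6 + 1/54) = 1.21 SD

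**Step 5: taxonomy.** This needs no arithmetic. Sections 5.4.2 and 6.6 define beneficial and harmful taxa by species, and 6.6.3 tests their gain or loss by ANOVA or Wilcoxon tests. Section 6.6.1 limits reliable assignment to genus. The two statements are not reconciled.

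**The case against.** **Separate evaluation.** Sections 3.1 and 6 say that the two sub-studies are analysed separately. Under that rule, a split at BMI 25 is possible only among the smokers, which is the analysis recommended here. This has weight, but it makes Question 2 ambiguous and does not settle it. Question 3 has to cross the sub-studies, so the rule has exceptions within the same section, and Question 2 refers to individuals without limit.

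**Awareness.** The Question 3 caveat refers back to Question 2 and implies that there are no lean non-smokers. That limitation is disclosed for Question 3, so redesigning Question 3 is optional. It does not tell a reader of Question 2 that its lean group consists entirely of smokers.

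**Low stakes.** Sections 2.1 and 3.1 call the study mainly exploratory. This comparison is reported through plots, with PCA and correlation as options, and no effect estimate is planned for it. That stands and limits the seriousness. Confounded plots can still be misread, and the distinction is a listed secondary endpoint. The covariate language in section 6 does not repair it, because it concerns mixed-effects models, which are not planned for this comparison.

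**Genus-level reporting is partly planned.** Question 1 in 6.6 also asks about genera, and 6.6.3 offers heatmaps by genus or family. This is true, but the named beneficial and harmful taxa remain species.

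**A stronger reading to avoid.** A reader might infer that BMI and smoking are fully confounded and that Question 2 cannot be answered from this study. The SAP does not support that. Smokers with BMI 25 to 35 are placed in the smoking sub-study, so lean and heavier women can be compared among smokers. Full confounding would require a smoking sub-study with no woman at or above 25, which the rules do not imply.

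**Conclusion.** The point holds as a fault in how the comparison is specified. Followed literally, Question 2 is heavily confounded with smoking, and the SAP neither restricts it, adjusts it nor warns about it. Under the assumptions stated, the pooled contrast carries 69% to 95% of any smoking effect, and about 80% if half of the smokers are lean. These figures rest on the planned numbers of 60 and 120, an unknown lean share, additive effects and no smokers in the diet sub-study. Light smokers in the diet arm would lower the shares somewhat. The absence of lean non-smokers follows from the eligibility rules alone.

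The BMI question remains answerable among smokers, with low precision, and the answer cannot be extended to non-smokers. The conflict between species and genus is real but secondary. Neither issue affects the primary endpoint, and the confounding does not affect the before-after microbiome analysis. The wording should be corrected before analysis.

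**What to change.** - In 6.6, Question 2, state that BMI below 25 against 25 or above at month 0 is compared within the smoking cessation sub-study only. Alternatively, pool and adjust for recorded smoking status.
- Add that the result applies to smokers only, because the design contains no lean non-smokers.
- Carry the same restriction into 6.6.3 and the baseline microbiome row of 6.16.
- In 5.4.2, 6.6 and 6.6.3, report beneficial and harmful taxa at genus level and label any species name as unconfirmed.

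This changes SAP wording only and needs no new samples. The cost is fewer women in Question 2, with a detectable difference of about 0.72 SD in the best case (30 vs 30) and 1.21 SD at 6 vs 54, together with a narrower target population and a coarser taxonomic claim.

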#### 6.6.3 Secondary outcome reporting

To report on the distinction of lean and obese/overweight individuals and smokers and nonsmokers, principal component plots will be generated and species plots will be provided.

To evaluate species diversity before and after intervention, richness indices such as the Shannon Diversity or inverse Simpson index will be reported before and after intervention. The relative gain or loss of beneficial and harmful individuals will be reported using ANOVA or Wilcoxon tests and visualised with barplots, and association of relative change could be associated with changes in epigenetic markers, BMI, or e.g. markers of gut leakiness (LBP).

A shift in dominant types and the association with stronger weight loss or epigenetic markers will be evaluated using heatmaps (e.g. the top 30 ASVs/genera/families). Subgroups of individuals where this shift does not occur will also be evaluated.

Functional pathway prediction will be done in R using the Tax4Fun2 package, evaluating pathways such as carbohydrate degradation, lipid metabolism, inflammatory properties, and hormone metabolism. A comparison may be conducted between individuals with and without ketogenic supplement in the diet intervention group.

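### The smoker versus non-smoker microbiome comparison is not restricted or adjusted for BMI, so a BMI difference can be mistaken for a smoking difference

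*SAP*

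**What the plan says.** The comparison is question 3 of SAP section 6.6: "Taxonomic composition of smokers and non-smokers will be analysed, with the caveat that non-smokers are all of BMI above 25". The sentence goes on to concede that this is something "which may have an impact on microbiome (see above"), which points back to question 2 on lean versus overweight women.

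The imbalance comes from the entry criteria in section 4.1.1. The diet criterion is "Dietary intervention: BMI between 25 and 35". The smoking criterion asks for at least 10 "cigarettes per day for at least the last five years" and sets no BMI limit. For women who meet both, the rule is: "Should 3 and 4 apply, the participant will be allocated to the smoking cessation group".

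Reporting is set in section 6.6.3: "To report on the distinction of lean and obese/overweight individuals and smokers and nonsmokers, principal component plots will be generated", together with species plots. The summary table in section 6.16 lists the contrast as a baseline comparison in fecal samples. That table is broken in the text available, so nothing is inferred from its adjustment column.

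**The concern.** The two groups differ on BMI by design, and the SAP itself treats BMI as a plausible driver of the same outcome. Any taxon or diversity measure that differs between lean and overweight women will tend to separate the groups even if smoking has no effect. A caveat tells the reader that the bias may be there but neither removes nor measures it.

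Disclosure might be enough if nothing better were possible, but here something better is. Women who meet both entry criteria go to the smoking arm, so smokers in the diet arm's BMI range can be expected. Section 8 shows that BMI and smoking status are recorded for all participants.

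A smaller issue is that section 6.6 does not say how a non-smoker is identified. The diet criterion does not exclude women who smoke fewer than 10 cigarettes a day or have smoked for under five years, so diet-arm membership does not guarantee non-smoking.

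**Working it through.** **The plan's own figure.** The SAP gives no power or error rate for this question. Its only power figure (section 3.6) concerns change in the methylation indices. It reproduces as Φ(0.2/0.44 × √60 − 1.96) = Φ(1.56) = 0.94, but has no bearing here.

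**Does any section deal with BMI for this contrast?**
- Section 6.6, question 3: caveat only.
- Section 6.6, question 1: brings in BMI, but for the month 0 to month 6 comparison.
- Section 6.6.2: PERMANOVA is optional and is described for interventions; no BMI term is named.
- Section 6.6.3: plots, with no BMI stratum or covariate.
- Section 6: non-intervention covariates will be explored and may enter mixed-effects models. This is optional, and it is tied to models not planned for this baseline contrast.

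No section commits to restriction, stratification or adjustment.

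**Illustration of size.** From the SAP: 60 smokers and 120 diet-arm women (section 3.1), significance level 0.05. Assumed, because the SAP gives neither: the share f of smokers with BMI below 25, and the lean versus overweight shift e in SD units. The true smoking effect is set to zero.

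Spurious difference = f × e. Standard error = √(1/60 + 1/120) = 0.158. Noncentrality = f × e / 0.158. The rejection rate is from a two-sided two-sample t test with 178 degrees of freedom.

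| f | e | f × e | Noncentrality | Rejection rate |
|---|---|---|---|---|
| 0.2 | 0.5 | 0.10 | 0.63 | 0.10 |
| 0.4 | 0.5 | 0.20 | 1.26 | 0.24 |
| 0.5 | 0.5 | 0.25 | 1.58 | 0.35 |
| 0.6 | 0.5 | 0.30 | 1.90 | 0.47 |

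The result depends heavily on e. At f = 0.5, a shift of 0.3 SD gives 0.16 and a shift of 0.8 SD gives 0.71. Allowing for the extra variance from mixing lean and overweight smokers lowers these only slightly (0.34 in place of 0.35 at f = 0.5, e = 0.5).

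**Cost of restriction.** Take a true smoking difference of 0.5 SD and 120 comparators, with noncentrality 0.5/√(1/n + 1/120):
- n = 60 smokers: 0.5/0.158 = 3.16, power 0.88.
- n = 30 smokers (half lean, none above BMI 35): 0.5/0.204 = 2.45, power 0.68.

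**The case against.** The strongest reply is that the SAP already states the limitation next to the question, plans only plots, and calls the study predominantly exploratory. On that view the rejection rates belong to a test the SAP does not commit to, and rest on two assumed inputs. This stands as a limit on the weight of the point. The rates show what a formal test would face and are not the error rate of a planned analysis.

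A reader might infer three stronger claims, none of which the document supports:
- **That a BMI difference will be reported as a smoking signature.** The SAP attaches the opposite warning, so it supports only that one can be mistaken for the other.
- **That restriction to BMI 25 to 35 removes the problem entirely.** That holds only if BMI has no effect within the range, or is distributed alike in both groups there. Neither can be known from the SAP.
- **That light smokers in the diet arm will be counted as non-smokers and dilute the contrast.** Section 6.6 does not define non-smoker by arm, and section 8 lists smoking status as current, ex or never. The definition is open, but the misclassification is an inference.

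It is also fair to say that restriction is not the only valid remedy, and that it discards an unknown number of smokers. None of this answers the core point: a caveat leaves smoking and BMI entangled when data to separate them, at least in part, are already collected.

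**Conclusion.** The point holds in a limited form. By the entry criteria, smokers of any BMI are compared with non-smokers who all have BMI above 25, and the plan has no step that separates the two factors. Question 3 cannot be answered from the unrestricted contrast.

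The direction of the problem follows from the document; its size does not. The range of about 10% to 47% assumes a lean share of 20% to 60%, a 0.5 SD BMI effect that acts as a step at 25, and a formal test that section 6.6.3 does not specify. With few lean smokers or a weak BMI effect, the distortion would be small. Smokers with BMI above 35, whom the criteria do not exclude, are not modelled.

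This is a secondary, exploratory question, and the primary endpoint is untouched.

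**What to change.** In section 6.6, question 3, and section 6.6.3:

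1. Make the main month 0 comparison either one restricted to women with BMI 25 to 35 on both sides, or one adjusted for BMI, for example with BMI as a term in any PERMANOVA. If adjustment is chosen over all smokers, state that there are no non-smokers below BMI 25, so that part of the adjustment rests on the model. Under restriction, report the BMI distribution of both groups so that any remaining imbalance can be seen.
2. Define smoker and non-smoker by recorded baseline smoking status and not by study arm, and say where ex-smokers are placed.
3. Keep the unrestricted principal component and species plots, labelled as descriptive only.

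The change is to SAP wording and needs no new data. The cost is precision under restriction: fewer smokers, with power for a 0.5 SD difference of about 0.68 with 30 smokers against 0.88 with all 60. The number actually retained depends on the BMI distribution of the smoking arm, which the SAP does not give.
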